**12.3 Demographic and Baseline Characteristics**

Baseline and demographic characteristics will be summarized by dose level. Continuous variables will be summarized using descriptive statistics (n, mean, standard deviation, median, minimum, and maximum). Categorical variables will be summarized with frequency tables.

**12.4 Efficacy Analyses**

Since the primary objective of this study is to evaluate the safety, tolerability, MTD, and clinically active dose of NS-018 in patients with PMF, post-PV MF, or post-ET MF, no formal hypothesis testing will be performed for efficacy parameters. Efficacy analysis will be based on the Efficacy Population.

The responses to treatment assessed using the IWG consensus criteria(Phase I) and the IWG MRT and ELN Response Criteria (Phase II)will be tabulated by dose level and visit. The number and percentage of patients achieving the response will be provided for each response level. The objective response rate (the percentage of patients with confirmed complete remission (CR), partial response (PR), or clinical improvement (CI) during the treatment period) and its 95% exact binomial confidence interval will be provided by dose level. Quality of life assessed using the MF SAF (Phase I) or MPN SAF (MPN-10) (Phase II) will be summarized by dose level and visit. Change in spleen size by MRI (CT scan for patients not able to tolerate MRI) for the Phase 2 portion will be summarized for the cohort.

**12.5 Safety Analyses**

All safety analyses will be based on the Safety Population. Adverse events, vital sign measurements, clinical laboratory information, ECG measurements, and concomitant medications will be summarized by dose level.

Adverse events will be coded using the Medical Dictionary for Regulatory Activities (MedDRA) classification system. The severity of all AEs will be graded according to the NCI CTEP CTCAE version 4.0. A summary of all AEs will be provided by system organ class and preferred term. The same summaries will be performed for Grade 3/4 AEs and drug-related AEs. Listings will be presented for SAEs, Grade 3/4 AEs, and AEs leading to discontinuation from the study.

Clinical laboratory evaluations at each visit and change from baseline (Cycle 1 Day 1) will be summarized by dose level. A laboratory value shift table will be provided. Vital signs and ECG parameters at each assessment time will be summarized by dose level. Other safety variables and their changes from baseline (when applicable) will be summarized by dose level at each of the scheduled assessment times.

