5.1.6 Phase 1: Cycle 7 and 10, Day 1, ( $\pm 1$  week)

If a patient remains on study drug beyond 4 cycles, he/she will only be required to return to the clinic every 3 months

- Directed physical examination including weight and spleen size by palpation;
- Vital signs (blood pressure, pulse, respiratory rate, and temperature; pre-dose);
- Laboratory tests (hematology, serum chemistries, and urinalysis, as listed in Appendix G);
- ECG – triplicate (pre-dose, locally read);
- Bone marrow assessment (pre-dose), Cycle 7 only;
- Response assessment (IWG-MRT);
- JAK2 V617F allele burden if mutation present prior to start of therapy (pre-dose);
- MF SAF (pre-dose);
- Review patient study drug dosing diary for compliance and distribute study drug, Cycle 7 only;
- Assessment of AEs using the NCI CTEP CTCAE, version 4.0 (published 28 May 2009) (see Appendix H); and
- Concomitant medication notation.

5.1.7 Phase 1: Cycle 8, 9 11 and 12 Day 1( $\pm 3$  days)

- Hematology and serum chemistry are to be obtained at the referring/local doctor's office and faxed to the study site, unless the patient is scheduled for a site visit.

5.1.8 Phase 1: Cycle 13, Day 1 and Day 1 of every 3 cycles thereafter ( $\pm 1$  week)

- Directed physical examination including weight and spleen size by palpation;
- Vital signs (blood pressure, pulse, respiratory rate, and temperature; pre-dose);
- Laboratory tests (hematology, serum chemistries, and urinalysis, as listed in Appendix G);
- ECG – single reading (pre-dose, locally read);
- Bone marrow assessment (pre-dose) Cycle 13 only, then annually;
- Response assessment (IWG-MRT);
- JAK2 V617F allele burden if mutation present prior to start of therapy (pre-dose);
- MF SAF (pre-dose);
- Assessment of AEs using the NCI CTEP CTCAE, version 4.0 (published 28 May 2009) (see Appendix H); and
- Concomitant medication notation.

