# If a DLT is experienced at any dose level, an intermediate cohort at a lower dose may be considered, as recommended by Safety Review Committee										
§ Additional cohorts at doses > 400 mg BID (800 mg/day) may be considered by the Sponsor if agreed by the Safety Review Committee after review of PK, PD, and safety data. The maximum planned increase in dose between cohorts will be 200 mg as the total daily dose (e.g., the dose level above 400 mg BID will not exceed 500 mg BID )										

During the study, a Safety Review Committee will review data from each cohort and may make dosing schedule changes based on the data review. The Safety Review Committee is described in detail in Section 13.9.

In the Phase 1 portion of the study, sequential cohorts of 3 to 6 patients will be treated with escalating doses until the MTD is established (see Section 6.1.1.3). The first patient in each cohort must be observed for at least 7 days of dosing with NS-018. If there is no clinically significant toxicity observed in that patient, enrollment in the cohort may continue. If a significant toxicity occurs, including any possible dose-limiting toxicity (DLT, see Section 6.1.1.2), the Safety Review Committee must meet and determine whether additional patients may be entered at that dose or an intermediate cohort at a lower dose should be considered. Each cohort can be assessed after at least 3 patients have completed 28 days of study drug dosing.

The Safety Review Committee can make dosing schedule changes (twice daily dosing rather than once daily dosing; intermediate dose levels if toxicity occurs that does not rise to the level of a DLT) based on pharmacodynamic, pharmacokinetic, and safety review. If twice daily dosing requires evaluation, dosing would start at one total daily dose level below the last once per day dose level that was declared safe. For example, when 300 mg QD was declared safe,

the starting dose for BID dosing would be 100 mg twice daily, 12 hours apart [representing a total daily dose 200 mg]).

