When the MTD is reached, the Phase 2 portion of the study will commence. Additional patients will be added at the MTD level to confirm tolerability and explore efficacy, for a total of 20 patients. Consideration by the Safety Review Committee will also be given to suspending Phase 2 enrollment at the MTD, and instead adding the same total number of patients at a second dose level, the CAD. The CAD is defined as a dose level below the MTD with a clinically significant response rate and an acceptable toxicity profile as determined by the

investigator/medical monitor and sponsor. The expansion cohorts for the MTD and CAD, should they both be pursued, will not be concurrently open for enrollment. The two dose levels would instead be expanded sequentially. Consideration will also be given to enroll patients only at the CAD but not MTD level, based on the risk/benefit of therapy as judged by the investigator/medical monitor and sponsor. After Phase 2 has started, patients who are continuing treatment from the Phase 1 portion of the study are able to change to the Phase 2 dose as intrapatient dose escalation, and based on risk/benefit as judged by the investigator. A change of schedule is allowed, such as a change from a QD Phase 1 dose to a BID Phase 2 dose. Since a patient could potentially be escalated by more than one dose upon crossing over from Phase 1 to the Phase 2 dosing schedule, the eligibility of the patient for dose escalation would be reviewed and the dose level determined by the investigator and the medical monitor. A patient must receive at least 3 months of study drug at the Phase 1 dose and not experience any Grade 3 or 4 drug-related toxicity before being escalated to the Phase 2 dosing schedule.

During the Phase 2 portion of the study, the Safety Review Committee will meet when a DLT-equivalent AE occurs, in order to determine whether additional patients may be enrolled at the same dose level or at a lower dose thereafter. In addition, the Safety Review Committee will meet when the number of patients completing Cycle 1 reaches 10 to review the pooled safety information to determine if further enrollment is warranted. Any DLTs that occur at a dosing schedule will be evaluated separately.

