**8.1.2 Definition of Adverse Events**

An AE is any untoward medical occurrence that occurs in a patient or clinical investigation subject administered a pharmaceutical product, and which does not necessarily have to have a causal relationship with this treatment. An AE can therefore be any unfavorable and unintended sign (including abnormal laboratory finding), symptom, or disease temporally associated with the use of an investigational product, whether or not considered related to the product.

Progression of disease is considered an efficacy outcome parameter and should not be captured as an AE.

All AEs, including intercurrent illnesses, occurring during the study will be documented in the eCRF. Concomitant illnesses, which existed before entry into the study, will not be considered AEs unless they worsen during the treatment period. All AEs, regardless of the source of identification (e.g., physical examination, laboratory assessment, ECG, reported by patient), must be documented.

Pre-existing conditions will be recorded in the eCRF on the Medical History or appropriate page.

A treatment-emergent AE (TEAE) will be defined as an AE that begins or that worsens in severity after at least one dose of study drug has been administered.

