## **12 STATISTICS**

Additional statistical analyses, other than those described in this section, may be performed if deemed appropriate. A description of the statistical analysis performed on the study data will be outlined in the Statistical Analysis Plan.

Each phase of this study will be analyzed separately. All tables, figures and listings will therefore be separated by study phase.

Interim analyses of PK, PD, and safety data from the Phase 1 portion of the study will be conducted after the MTD has been established.

An analysis of all existing PK, PD, and safety data from the Phase 2 portion of the study will be conducted 6 months after the last patient is enrolled in this part of the study.

The complete analysis of all study data will be contained in the clinical study report at the end of the study.

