### **13.9 Safety Review Committee**

A Safety Review Committee, consisting of the actively recruiting investigators, the medical monitor overseeing the study for NS Pharma and a NS Pharma representative will meet to evaluate each cohort. If clinically significant toxicity occurs in the first patient in any cohort during their first 7 days of NS-018 dosing, the Safety Review Committee will meet and determine dosing for future patients. The Safety Review Committee must review each cohort before patients can be enrolled into the next cohort. The Safety Review Committee can make dosing schedule changes (twice daily dosing rather than once daily dosing; intermediate dose levels if toxicity occurs that does not rise to the level of a DLT) based on pharmacodynamic, pharmacokinetic, and safety review. If twice daily dosing requires evaluation, dosing would start at one total daily dose level below the last once per day dose level that was declared safe.

If DLTs are seen in the 75 mg cohort, a cohort, labeled -1 and dosed at 50 mg, may be considered by the Safety Review Committee. Cohorts at doses >400 mg BID(800 mg/day)may be considered by the Sponsor if agreed by the Safety Review Committee after review of PD, PK, and safety data. The maximum planned increase in dose between cohorts will be 200 mg as the total daily dose (e.g., the dose level above 400 mg BID will not exceed 500 mg BID).

Should BID dosing commence during the Phase I portion of the study, the SRC will meet after the last patient in that cohort has completed 28 days of dosing to assess the safety of that dosing schedule. Should the BID cohort be declared safe, the next BID cohort may begin. BID cohorts and QD cohorts may enroll simultaneously provided the previous lower dose of each cohort type has been declared safe by the SRC.

During the Phase 2 portion of the study, the Safety Review Committee will meet when a DLT-equivalent AE occurs, in order to determine whether additional patients may be enrolled at the same dose level or at a lower dose thereafter. In addition, the Safety Review Committee will meet when the number of patients who have completed Cycle 1 reaches 10 to review the pooled safety information to determine if further enrollment is warranted.

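### AE percentages by dose level have no common time window, exposure adjustment or attribution rule, so they can understate or reverse a dose-toxicity trend

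*Combined protocol and SAP*

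**What the plan says.** Section 12.5 groups safety data by dose level: "Adverse events, vital sign measurements, clinical laboratory information, ECG measurements, and concomitant medications will be summarized by dose level". For AEs it adds: "A summary of all AEs will be provided by system organ class and preferred term", and repeats this for Grade 3/4 and drug-related events. No period is named. In the same section, laboratory values are summarized at each visit, and vital signs and ECGs at each assessment time. AEs are the main safety outcome there without a time axis.

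The surrounding text leaves the AE period open. In Section 8.1.2, "A treatment-emergent AE (TEAE) will be defined as an AE that begins or that worsens in severity after at least one dose" of study drug; the definition gives no closing date. Section 13.10 lets treatment run on while the patient benefits. Section 6.1.1 sets the order of enrolment: "sequential cohorts of 3 to 6 patients will be treated with escalating doses until the MTD is established". Section 12 sets the data cut: "Interim analyses of PK, PD, and safety data from the Phase 1 portion of the study will be conducted after the MTD has been established".

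Section 6.1.1 also permits intrapatient escalation after at least 3 months at a dose, under conditions. Section 12.5 does not say whether a later AE then counts under the assigned dose or the dose at onset.

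Phase 1 AE visits are weekly in Cycle 1 and 4-weekly to Cycle 4 Day 1. For patients staying on drug after that, Section 5.1.6 says "he/she will only be required to return to the clinic every 3 months".

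**The concern.** A crude percentage with at least one AE rises with time observed as well as with toxicity. If the lowest dose opened first and the cut comes soon after the highest dose was tested, the two percentages cover different lengths of time. An equal event rate at all doses then shows as incidence falling with dose, and a moderate true increase can be hidden or reversed.

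Safety and tolerability are primary objectives in Phase 1. The clinically active dose is defined in Section 6.1.1 as a dose below the MTD with "a clinically significant response rate and an acceptable toxicity profile as determined by the" investigator or medical monitor and the sponsor. The by-dose AE tables are a natural source for that judgement, although the protocol does not say they are its basis.

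**Working it through.** **The plan's own figures.** The plan gives no figure for AE incidence by dose. Its only computed figures are the Phase 2 detection probabilities in Section 12.1. From 1 − (1 − p)^20 they reproduce: 64.2%, 87.8%, 96.1%, 98.8% and 99.9% at 5, 10, 15, 20 and 30%. They are not in dispute.

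**Inputs from the protocol.** Section 6.1.1 requires 7 days' observation of the first patient in a cohort, and allows assessment once at least 3 patients have completed 28 days. The minimum per cohort is 7 + 28 = 35 days. The dose table lists four BID cohorts, and the QD cohorts are marked completed.

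**Assumptions, not in the documents.** The AE hazard h is constant and the same at every dose, at 5% or 10% per 28 days. Nobody stops or changes dose. The cut falls when the top cohort completes its 35 days.

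**Formula.** Crude incidence = 1 − exp(−h × days/28).

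| BID cohort | Potential follow-up (days) | h = 5% | h = 10% |
|---|---|---|---|
| 1 (lowest) | 4 × 35 = 140 | 22% | 39% |
| 2 | 3 × 35 = 105 | 17% | 31% |
| 3 | 2 × 35 = 70 | 12% | 22% |
| 4 (highest) | 35 | 6% | 12% |

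Follow-up is counted from each cohort's first dose. Patients who start after the 7-day hold have 7 days less in every cohort; at 5% this gives 21% against 5%.

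**A true dose effect.** Double the hazard at the top dose, with 5% at the lowest. The top gives 1 − exp(−0.10 × 35/28) = 12% against 22%, so the order is reversed. Because 140/35 = 4, a fourfold hazard is needed before the top dose matches the lowest. Restricted to Cycle 1, the doubled hazard gives 1 − exp(−0.10) = 9.5% against 1 − exp(−0.05) = 4.9%, the right order.

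**Patients added at the previous dose.** Section 6.1.1.3 requires at most 1 of 6 with a DLT at the MTD and at least 2 with a DLT at the next dose. If the top cohort exceeds the MTD and the cohort below has 3 patients, 3 more are treated there for at least 28 days. Follow-up becomes 168 and 133 days in cohorts 1 and 2; 98 days for 3 patients and 28 days for 3 patients in cohort 3; and 35 + 28 = 63 days in cohort 4. At 5%:

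- Cohort 1: 1 − exp(−0.30) = 26%.
- Cohort 2: 1 − exp(−0.2375) = 21%.
- Cohort 3: mean of 16.05% and 4.88% = 10.5%.
- Cohort 4: 1 − exp(−0.1125) = 10.6%.

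The top two are now level (19.5% and 20.1% at h = 10%). The lower doses still stand above them. With a doubled hazard the top dose gives 1 − exp(−0.225) = 20% against 26% at the lowest, so that order is still reversed.

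**Shorter time at low doses (h = 5%).**

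- Discontinuation of 10% per cycle, m = −ln 0.9 = 0.105. Incidence is h/(h + m) × [1 − exp(−(h + m) × days/28)], which gives 17% at 140 days and 6% at 35.
- Lowest-dose time capped by escalation at 3 cycles (84 days): 1 − exp(−0.15) = 14% against 6%.

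**Visit schedule.** Phase 1 gaps between AE visits are 7, 7, 7, 7, 28 and 28 days, then 84. The schedule is the same for every dose level, apart from one extra visit a month after an intrapatient escalation.

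**The case against.** A reader might infer that lower-dose cohorts are in fact followed longer and that the by-dose tables are distorted as a result. The documents do not support that. Longer low-dose follow-up is potential only. Section 4.4 stops patients without clinical benefit after 6 cycles, Section 6.1.1 lets patients escalate out of a low dose, and Section 13.9 says "BID cohorts and QD cohorts may enroll simultaneously provided the previous lower dose of each cohort type has been declared safe by the SRC". Each can shorten the lag. None removes it in the BID illustration: 6 cycles is 168 days, not less than the potential follow-up in either version, and BID cohorts remain sequential among themselves. Escalation narrows the gap but makes the missing attribution rule more important.

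A reader might also infer that thinning AE visits bias the dose comparison. They do not in themselves, because all Phase 1 doses share the schedule. Sparser late ascertainment would partly offset the inflation from long follow-up, and the figures above ignore that. Patients also report AEs between visits (Section 8.1.4), and local laboratory tests continue.

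Nor do the documents show that dose escalation rests on these tables. The Safety Review Committee reviews each cohort around 28 days, and the MTD uses DLT counts. The MTD table's heading counts DLTs during study treatment without a window, which should be reconciled with the 28-day review.

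Precision is poor in any case. In a cohort of 3, 22% against 6% is 0.7 against 0.2 patients; in a cohort of 6, 1.3 against 0.4. The exact 95% interval for 1 of 6 is 0.4% to 64%. Small numbers limit what any table can show, but they do not make unequal windows comparable.

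Finally, Section 12 defers detail to a Statistical Analysis Plan. No separate SAP text is in the document, so the gap may be closed there.

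**Conclusion.** The point holds as a risk to comparability. Reading the AE tables as covering all time on treatment is the default reading of Section 12.5, not an explicit statement. On that reading, with sequential cohorts, open-ended treatment and a cut once the MTD is set, crude AE percentages by dose can understate or reverse a dose-toxicity trend.

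The illustration is 22% against 6% under an equal hazard of 5% per 28 days (39% against 12% at 10%). It becomes 26% against 11%, with the top two doses level, once patients are added at the previous dose. These figures rest on a constant hazard, full detection, minimum cohort length and no dropout or escalation. Real size and direction depend on actual time on dose, discontinuation and escalation. The concern is confined to AEs; laboratory, vital-sign and ECG summaries already follow a time axis. A change is worth making because a better table can be built from data already collected.

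**What to change.** In Section 12.5, or in the SAP it relies on:

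1. Add a Cycle 1 table of all AEs and of Grade 3 or higher AEs by initially assigned dose, as the main table for comparing doses. Keep patients who stop during Cycle 1 in the denominator. Every cohort has the same window and visit schedule there, and the 3-month requirement means no intrapatient escalation has yet occurred.
2. Report duration of exposure by dose level. Give AEs per patient-cycle as supportive only: ascertainment is sparser later, so these rates would tend to fall with longer follow-up.
3. State how AEs are attributed after a dose change, whether to the initially assigned dose or the dose at onset.
4. Keep the all-time AE table, with a note that follow-up differs by dose level. It is still needed for late toxicity.

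The cost is wording and a few extra descriptive tables, with no new data collection. The Cycle 1 table does not capture late toxicity, which is why the all-time table stays beside it.

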## **12.6**

### **Pharmacokinetic Analyses**

Blood samples for PK analysis of NS-018 and its metabolites will be collected at designated study visits. All PK analyses will be based on the PK population.

Plasma concentrations of NS-018 and its metabolites will be summarized descriptively by dose level and time point of collection. Summary statistics including number of patients, arithmetic mean, geometric mean, geometric CV, standard deviation, minimum, maximum, median, coefficient of variation, and standard error of the mean will be presented. Individual patient and mean plasma concentrations of NS-018 and its metabolites will be plotted vs. time in linear and log-linear scale.

Derived PK parameters will be listed and summarized using the same measures as for the plasma concentrations of NS-018 and its metabolites.

#### **12.6.1**

##### **Relationship between PK data and endpoints**

The relationship between plasma concentrations of NS-018 and its metabolites and each efficacy and toxicity outcome measure as well as any biomarker endpoints will be explored. The details will be outlined in the Statistical Analysis Plan.

## **12.7**

### **Pharmacodynamic Analyses**

All PD analyses (JAK2 V617F allele burden, phospho-STAT3, and cytokine levels) will be based on the PD Population. JAK2 V617F allele burden and phospho-STAT3 values and cytokine levels at each time point and changes from baseline will be summarized descriptively by dose level and listed. The relationship between NS-018 dose level and JAK2 V617F allele burden or phospho-STAT3 levels over time will be explored.

